## INTRODUCTION

The population-based rate of mild traumatic brain injury (mTBI) is estimated to exceed 600/100000 population per year in total, if including only patients seeking emergency care the estimated rate is approximately 100-300/100000 (1). Many patients recover within 3 months after injury but a sustainable proportion suffer from persisting symptoms, for instance fatigue, headaches, irritability (2).

Early identification of people at risk for long-term consequences after mTBI is important in order to arrange appropriate follow-up and treatment but due to the heterogeneity and non-specificity of the symptoms after mTBI this is not a simple task (3). A large prospective study found that 44 % of the patients showed incomplete recovery 6 months after injury, also noting that previous mental health problems and lesser education were related to worse outcome, whilst CT abnormality was not (4).

As conventional neuroimaging techniques have failed to detect the subtle alterations that may be important for prognosis and long-term outcome after mTBI, studies using fMRI have shown some interesting results (5, 6). Resting-state fMRI (rs-fMRI) measures functional connectivity, which may be disrupted by the effects of mTBI, by investigating co-activation patterns between distinct brain regions, when an explicit task is not being performed. Several studies have shown signs of hyper connectivity after mTBI, but the results are inconclusive regarding if hyperconnectivity is related to better or worse outcome (3). It is suggested that other variables, for instance demographic and cognitive variables, also need to be incorporated with imaging biomarkers when investigating the relationship between fMRI biomarkers with outcome after mTBI (3).

A marker related to demographic status and cognition that have shown to be relevant for outcome in brain injury or pathology is cognitive reserve (7). Cognitive reserve is defined as an aspect of the brain's function or structure that impacts the relationship between injury/pathology and outcome (8). Higher cognitive reserve is related to better outcome in conditions ranging from Alzheimer, MS and mTBI (9-11). Cognitive reserve is inherently abstract and hence measured by proxy measures such as length of education or tests of intelligence (8).

## AIM/OBJECTIVES

To investigate whether change in connectivity over time after mTBI, according to fMRI, varies depending on cognitive reserve compared to orthopedic controls and how this is related to symptoms and symptom resolution.

## METHODS

## STUDY SETTING

Patients were recruited from the emergency department at Danderyd Hospital between January 2015 and April 2016. Baseline and follow-up assessments, including MRI scans were conducted at Danderyd University Hospital.

## PATIENT CHARACTERISTICS

15 patients with mTBI and 15 controls with a minor orthopedic injury were recruited. The orthopedic controls were in the same age span and consisted of patients of with minor traumatic injuries to the hand, arm, foot or leg with no need of surgical intervention.

## ELIGIBILITY CRITERIA

Eligible patients in the mTBI group were consecutive patients, between 18 and 40 years of age, presenting at the emergency department at Danderyd Hospital (Stockholm, Sweden) between January 2015 and April 2016 due to an mTBI to such an extent that CT was indicated. mTBI was defined by a Glasgow Coma Scale (GCS, (12)) score between 13-15 and one or more of the following symptoms: <30 minutes loss of consciousness, <24 hours post-traumatic amnesia and/or a transient neurological deficit according to the WHO Collaborating center of Neurotrauma Task Force (13). Exclusion criteria were uncertain duration of loss of consciousness, if they had contraindications to MRI, if they had a previously acquired brain injury, a progressive neurological disorder or another injury/illness with short expected survival, if they were dependent of help in daily living before the current damage, if they had severe visual impairment or were non-Swedish speaking.

The orthopedic controls (OC; n = 15) were in the same age span and consisted of patients of with minor traumatic injuries to the hand, arm, foot or leg with no need of surgical intervention. These patients were non-systematically and intermittently included in the study during the same time frame as the mTBI patients. A prior history, within 2 years of the study, of a traumatic head injury in a need of medical attention was an exclusion criterion for controls.

## OUTCOME VARIABLES

Table 1: Outcome measures

Outcome measure	Measures
Primary outcome measures	
State fatigability	Difference between score during the first 60 and the last 60 seconds of the Digit Symbol Substitution Test/Coding (DSST, (14)). The lower the score, the stronger the indication of fatigability
Self-rated post-concussion symptoms	
	For assessment of self-rated symptoms The Rivermead Post-Concussion Symptoms Questionnaire (RPQ, (15)) was used. RPQ is based on a Likert scale and includes 16 items with ratings from 0 to 4. Higher score indicates more symptoms.
Secondary outcome measures	
Trait fatigability	The Fatigue Severity Scale (FSS (16)) was used to measure trait fatigue. FSS consists of 9 questions and is based on a 7 point Likert scale A high score implies a higher level of fatigue.

Anxiety and depression	Hospital Anxiety and Depression (HADS, (17)) scale was used to screen for depression and anxiety, higher scores indicate more severe problems
Self-rated visual symptoms in near work	Convergence Insufficiency Symptom Survey (CISS, (18)) was used to assess near work-related visual symptoms. Total score is 60 and a value above 21 indicates a high level of symptoms.
Visual disturbances	A visual examination performed by a licensed optometrist, using standard optometric clinical methods. Diagnosis of visual dysfunction were based on established diagnostic criteria (19).

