## RECRUITMENT AND ANALYSIS OF NON-PARTICIPANTS

Patients were recruited at the emergency department at Danderyd Hospital. Consecutive patients, seeking care for mTBI or a minor orthopedic injury were asked to participate in the study.

Subject recruitment was conducted between January 2015 and January 2016 and was stopped when a total of 15 patients with mTBI and 15 orthopedic controls were enrolled, in accordance with the power calculation.

Among the 129 patients who were asked for participation in the study (32 mTBI; 97 OC), a total of 99 people declined, 17 mTBI and 82 OC. Of those who declined, 88% of mTBI and 64% of orthopedic subjects were men, and there was no difference regarding age between participating and non-participating individuals. The reasons stated for not participating were lack of time and inconvenience. Two individuals in the mTBI group and two individuals in the orthopedic control group were lost to follow-up despite several follow-up phone calls and letters.

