#### **MEASURES**

##### *SELF-ASSESSMENT*

For assessment of self-rated symptoms The Rivermead PostConcussion Symptoms Questionnaire (RPQ, (15)) was used. RPQ is based on a Likert scale and includes 16 items with ratings from 0 to 4. A score of 1 means that the symptom has been present but is no longer a problem and a score between 2 and 4 indicates symptom severity from 'mild to severe.'

Self-rated trait fatigability were rated with the Fatigue Severity Scale (FSS, (16)). FSS consists of 9 questions and is based on a 7 point Likert scale A high score implies a higher level of fatigue. It is one of the most frequently

used inventories for measuring fatigue in people with chronic illnesses and is considered to have robust psychometric properties (20).

Occurrence of depression and anxiety were screened with Hospital Anxiety and Depression Scale (HADS, (17)). The scale comprises of two separate scales for anxiety and depression. Scores range from 0 to 21, with scores from 0 to 7 representing a “normal,” 8–10 a “mild,” 11–14 a “moderate,” and 15–21 a “severe” level of anxiety or depression. The HADS has been widely used to assess anxiety and depression following TBI (21).

Self-rated near work related visual symptoms were measured with Convergence Insufficiency Symptom Survey (CISS, (18)). The CISS is a validated and reliable instrument which assesses both direct symptoms (eg. blurred vision, double vision) and indirect symptoms (eg. difficulty maintaining concentration, headache)(18). The survey includes 15 questions with ratings from 0 “never” to 4 “always”. Total score is 60 and the cut-off score for abnormally high levels of symptoms is 21.

Visual disturbances were measured by a licensed optometrist, using standard optometric methods. Included in the assessment was tests of visual acuity, refractive error, stereoacuity, accommodation, heterophoria, eye motility and fusional vergence. Diagnosis of visual dysfunctions were based on established diagnostic criteria (19).

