Diagnosis of visual dysfunction was based on established diagnostic criteria. Visual functions were measured by a licensed optometrist, including assessment of refractive error, visual acuity, stereoacuity, heterophoria, fusional vergence, eye motility, near point of accommodation, and near point of convergence. A questionnaire, Convergence Insufficiency Symptom Survey (CISS), assessed visual strain during near work. Only convergence, accommodation, fusional vergence, and CISS will be analyzed in this project based on previous findings from the same dataset (22) and clinical experience.

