#### *NEUROPSYCHOLOGICAL ASSESSMENT*

The Digit Symbol Substitution Test/Coding (DSST, (14)) from the Wechsler scales, is primarily used for measuring psychomotor processing speed. The task is ongoing for 120 s during which the participant is expected to fill in symbols paired to digits. The score is the number of symbols correctly completed, higher score indicates better result. In this study DSST was used to measure Fatigability (DSST-f). DSST-f was calculated by subtracting the score for the first half of the test (60 first seconds) from the last part of the test (60 last seconds). A negative score implies a slower performance during the latter part of the test, which is indicative of fatigability(23). DSST-f has previously been demonstrated to be a sensitive measure for fatigability, but not depression, in patients with mTBI (24).

The Swedish Lexical Decision Test was used at to assess premorbid IQ. The Swedish Lexical Decision test measures the premorbid estimated full-scale intelligence quotient (IQ), based on that word knowledge and cognitive functioning generally are associated, and that this association are relatively unaffected by TBI (25). In this test, the subject must make a lexical decision by judging if target words are real or fictitious. The Swedish Lexical

Decision Test has been demonstrated to explain 48 % of the variance of full-scale IQ from the WAIS-R and 31 % of demographic variables alone (25). If used in combination with demographic variables the estimation of premorbid cognitive functioning is further improved (25).

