#### STATISTICAL ANALYSIS

Descriptive statistics will be used to depict demographics, injury characteristics, results on neuropsychological tests and psychological screening instruments. Multi-subject and multi-session analysis based on general linear model will be performed and assessed using statistical tools including regression analysis and 2-way ANOVA.

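### Does scoring a resolved RPQ symptom as 1 make the primary symptom outcome misstate symptom resolution?

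*Combined protocol and SAP*

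**What the plan says.** Table 1 under Outcome Variables lists the RPQ as one of two primary outcomes: "RPQ is based on a Likert scale and includes 16 items with ratings from 0 to 4. Higher score indicates more symptoms". The Self-Assessment section repeats the items and range and then gives meanings: "A score of 1 means that the symptom has been present but is no longer a problem", whereas "a score between 2 and 4 indicates symptom severity". The Aim/Objectives section asks whether change in connectivity varies with cognitive reserve, and "how this is related to symptoms and symptom resolution".

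Data Collection and Management sets two assessments, planned for 7–10 days and 75–100 days after injury and later widened. The Statistical Analysis section describes general linear models across subjects and sessions, "assessed using statistical tools including regression analysis and 2-way ANOVA". No section says whether RPQ items are summed, how a 1 enters a score, or which variable represents resolution.

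**The concern.** A 1 sits above a 0 on the rating scale, yet by the stated anchors neither is a current symptom. If higher always means more symptoms, a resolved symptom is treated as partly remaining.

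The rating in doubt is the resolved category, which is what the aim is about. Two harms would follow from a raw sum:

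- Recovery within a patient would look smaller than it was.
- At follow-up, a group with more resolved symptoms would score higher than a group with the same current symptoms. If the mTBI group has more resolved post-concussion symptoms than the orthopedic controls, which is plausible but not documented, this could pass for persisting symptoms.

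With no written scoring rule and a small sample, that would matter for a primary outcome.

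**Working it through.** The plan gives no RPQ-based figure to reproduce. Its only design calculation (12 per group, 80% power) concerns voxel-level activation and does not depend on RPQ scoring.

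**Inputs.** 16 items rated 0–4 (Table 1). Anchors for 1 and for 2–4 (Self-Assessment). 15 recruited per group (Patient Characteristics), less the losses: "Two individuals in the mTBI group and two individuals in the orthopedic control group were lost to follow-up". That leaves 15 − 2 = 13 per group.

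**1. One item.** Let a symptom start at rating b and resolve to 1. The raw fall is b − 1. With a 1 counted as 0, the fall is b. The visible share is (b − 1)/b.

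| Baseline rating b | Raw fall | Recoded fall | Share visible |
|---|---|---|---|
| 2 | 1 | 2 | 50% |
| 3 | 2 | 3 | 67% |
| 4 | 3 | 4 | 75% |

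The raw fall is positive for every b from 2 to 4, so resolution of a current symptom is understated but keeps its sign. The one movement in the wrong direction is 0 to 1, a symptom that arises and ends between visits, which adds 1 point. An item rated 1 at both visits cancels in a change score.

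**2. The total.** Sixteen resolved symptoms give 16 × 1 = 16 on a raw sum with maximum 16 × 4 = 64. That equals eight current mild symptoms (8 × 2 = 16) and exceeds seven (7 × 2 = 14). Sixteen mild symptoms that all resolve go from 32 to 16 raw, and from 32 to 0 recoded.

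**3. Does the plan commit to a raw sum?** Compare the scores that the text allows.

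| Score | All 16 resolved | Eight current mild | Fits the anchors? |
|---|---|---|---|
| Raw sum | 16 | 16 | No |
| Sum with 1 counted as 0 | 0 | 16 | Yes |
| Number of items rated 2–4 | 0 | 8 | Yes |

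Table 1 says score, which can mean a total. Under the second and third rows a higher score does mean more current symptoms, and Table 1 agrees with the Self-Assessment section. Only the first row conflicts, and no section prescribes it.

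**4. Group comparison.** Take a two-sided t test at 5% on follow-up scores, with 13 per group, 24 degrees of freedom and critical value 2.064. Let the groups have equal current symptoms, and let mTBI patients have m more items rated 1 on average. Then d = m/SD and the noncentrality is d × √(13/2). A false difference is found with these probabilities:

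| SD | m = 2 | m = 4 | m = 6 |
|---|---|---|---|
| 6 | 0.129 | 0.372 | 0.687 |
| 9 | 0.085 | 0.193 | 0.372 |
| 12 | 0.069 | 0.129 | 0.232 |

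The arithmetic is right, but m and SD are assumed because the documents hold no RPQ data. The test itself is also assumed: the plan names regression and two-way ANOVA over sessions, not a follow-up t test. In a group-by-visit contrast, more newly resolved symptoms in the mTBI group would shrink that group's measured fall. That weakens a real difference in change and does not produce the false persistence tabulated here.

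**5. Would a prescribed measure be better?** An obvious candidate is the recoded baseline total minus the recoded follow-up total. An item going from 4 to 2 contributes 2 points. An item going from 2 to 1 contributes 2 − 0 = 2 points. The first symptom is still current and the second is over, yet they count the same, and new symptoms offset resolved ones. This is net improvement, not resolution. Counting items rated 2–4 at baseline and 0–1 at follow-up is closer to the word but discards partial improvement. Both are defensible, and the documents do not favour either.

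**The case for a change.** The strongest case for a change is that an anchor is not a scoring rule. The RPQ is a primary outcome, the open point falls on the category the aim asks about, data collection is over while the analysis is written in the future tense, and a few sentences would close the gap. With about 13 per group, freedom to choose a score after seeing data is unwelcome. The visual measures were already narrowed "based on previous findings from the same dataset".

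Part of this stands. The plan does not write down how a 1 is scored, which visit or change is analysed, or what resolution means, and stating these before analysis would be good practice. The rest is weaker. The remark about earlier findings concerns visual measures only, and the documents do not say whether RPQ data had been examined. The scale is not shown to be wrong, because the harm arises only under a scoring choice that the plan never makes and that its own item anchors argue against.

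**Conclusion.** No change is called for. The two descriptions of the RPQ are compatible, and what remains is missing detail that analysts can fill from the stated anchors, by counting a 1 as no current symptom and deriving resolution from the two visits.

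If a raw sum were used regardless, a symptom resolving to 1 would show 50%, 67% or 75% of its full fall from a start of 2, 3 or 4. That is attenuation without reversal for symptoms current at baseline. The false-difference probabilities of about 7% to 69% should not be used to size the issue, because they rest on assumed inputs and an unplanned test.

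This conclusion assumes that the analysts follow the anchors in the Self-Assessment section and that item-level ratings exist at both visits, which the documents do not state. If only raw totals were kept, the attenuation above would apply and would be a limitation in interpreting the results.

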## SAMPLE SIZE

In order to detect differences in activation on a voxel level with alpha set to 0.05, 12 participants per group are needed to achieve 80 % power (20). 15 participants per group were recruited to compensate for expected attrition. The groups are matched regarding age, educational level and premorbid IQ.

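### The 80% power is stated for a voxel-level activation difference; the aim's contrast, reserve-by-group on connectivity change, has no power statement

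*Combined protocol and SAP*

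**What the plan says.** SAMPLE SIZE contains the plan's only power statement: "In order to detect differences in activation on a voxel level with alpha set to 0.05, 12 participants per group are needed", for 80% power. Fifteen per group were recruited to allow for attrition. The section gives no effect size, SD, sidedness or correction across voxels. The reference cited for the figure, number 20, appears in the reference list as a psychometric study of the Fatigue Severity Scale, so the basis of the 12 cannot be traced within the document.

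AIM/OBJECTIVES states the question: "To investigate whether change in connectivity over time after mTBI, according to fMRI, varies depending on cognitive reserve compared to orthopedic controls". The functional scan is resting-state only, which INTRODUCTION describes as measured "when an explicit task is not being performed".

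RECRUITMENT AND ANALYSIS OF NON-PARTICIPANTS says enrolment stopped at 15 and 15 "in accordance with the power calculation". It reports two people per group lost to follow-up, which leaves 13 per group for any analysis of change.

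STATISTICAL ANALYSIS names a general linear model, regression and 2-way ANOVA, but no reserve-by-group term. RESTING-STATE fMRI DATA PROCESSING ends with permutation testing of group differences.

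**The concern.** The powered quantity and the aim differ in three respects. The calculation concerns activation, while the aim concerns connectivity. The calculation does not mention change, while the aim is about change between two visits. The calculation implies a comparison of groups, while the aim asks whether the relation between reserve and change differs between groups, which is an interaction. At a given sample size an interaction is usually estimated less precisely than a group mean difference, so 80% for one cannot be carried over to the other.

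The risk lies in interpretation. Because recruitment is tied to the power calculation, a reader may take the study as adequately sized for its aim and read a null reserve result as evidence that reserve does not matter. Nothing in the plan supports that reading.

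**Working it through.** **Inputs from the document.** Alpha 0.05, power 80%, 12 per group (SAMPLE SIZE); 15 - 2 = 13 per group with follow-up (RECRUITMENT AND ANALYSIS OF NON-PARTICIPANTS).

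**Assumptions, because the document is silent.** Two independent groups, two-sided test, one measure with no correction, normal errors. Reserve is continuous and standard normal within each group. The between-visit correlation rho of connectivity is 0, 0.5 or 0.8.

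**Step 1: the plan's own figure.** With no effect size, 12 per group cannot be reproduced, only inverted. For a two-sample t test with noncentrality d × sqrt(n/2) and df = 2n - 2, 80% power at n = 12 requires d = 1.197. The same d gives 83% at n = 13 and 89% at n = 15. This d depends on the assumed design: a within-group test with 12 people implies d = 0.89, and a two-group test at a 0.001 threshold implies d = 1.93.

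**Step 2: the aim's contrast in units of the SD of change.** Let mTBI patients at +1 and -1 SD of reserve differ by 1.197 SD of change relative to controls. The slope difference is then 1.197 / 2 = 0.598 per SD of reserve. The test is t = (b1 - b0) / [s × sqrt(1/Sxx1 + 1/Sxx0)] with df = 2n - 4, where b1 and b0 are the two slopes and Sxx is the sum of squares of reserve in each group.

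With Sxx near n - 1 = 12, the standard error is about sqrt(2/12) = 0.41, so the effect is about 0.598 / 0.41 = 1.5 standard errors. The group mean contrast has standard error sqrt(2/13) = 0.39, so its effect is 1.197 / 0.39 = 3.1 standard errors. Simulation with reserve drawn at random gives power of 25% (n = 12), 27% (n = 13) and 31% (n = 15).

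**Step 3: if d is instead in cross-sectional SD units.** SD of change = SD × sqrt(2(1 - rho)), which is 1.414, 1.000 and 0.632 times the SD for rho = 0, 0.5 and 0.8. At 13 per group:

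| Contrast | rho 0 | rho 0.5 | rho 0.8 |
|---|---|---|---|
| Simple group contrast on change, d = 1.197 | 54% | 83% | over 99% |
| Reserve-by-group, d across 2 SD of reserve | 15-16% | 27-28% | 55-56% |
| Reserve-by-group, median split, d between halves | 18% | 31% | 64% |
| Reserve-by-group, d per 1 SD of reserve | 47% | 74% | 97% |

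In every column each reserve-by-group figure is below the simple contrast.

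**Step 4: what 13 per group can detect.** In units of the SD of change (residual SD 1), 80% power needs a slope difference of about 1.30 per SD of reserve. Equal and opposite slopes of 0.65 would give it, each a correlation of 0.65 / sqrt(1 + 0.65²) = 0.545. Because it is expressed in SD of change, this figure does not depend on rho.

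**The case against.** The strongest reply is that the document fixes no power for the reserve contrast, high or low. Sidedness, effect size, between-visit correlation and the form of reserve are all unstated, and the table runs from about 15% to 97%. That stands. A reader might infer that the study has 15% to 27% power for its aim, but such a figure is one corner of the range and must carry its conditions.

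It is also fair that SAMPLE SIZE never claims 80% for the reserve contrast. Its wording fits the group-difference test planned under RESTING-STATE fMRI DATA PROCESSING, and the interaction is read from the aim, not from a model the plan writes down. What remains is that the aim has no power statement while recruitment is justified by one.

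Other stronger readings are tempting but unsupported:
- *Shrinking the slope for proxy error.* The lexical test is said to "explain 48 % of the variance of full-scale IQ from the WAIS-R". Using that as an attenuation factor treats WAIS-R IQ as true reserve. No section does so: INTRODUCTION also names education as a proxy, and NEUROPSYCHOLOGICAL ASSESSMENT says that adding demographic variables improves the estimate.
- *Calling the figures best cases.* Lack of voxel correction is only one assumption; a high between-visit correlation raises power.
- *Saying any significant reserve result will be strongly exaggerated.* In simulation, significant estimates average about 1.8 times the truth at a slope difference of 0.60, but only about 1.1 times at 1.3.
- *Reading activation as proof of a task-fMRI calculation.* INTRODUCTION itself describes resting-state fMRI in terms of co-activation, so the word may be loose.

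**Conclusion.** The point holds in this form: the 80% belongs to a voxel-level activation difference and does not apply to the reserve-by-group contrast on connectivity change, for which the plan gives no power. That follows from the text alone.

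The size is conditional. Under a two-group, two-sided, uncorrected reading with d of about 1.2 in SD of change, placed between +1 and -1 SD of reserve, power at 13 per group is about 27%. With d in cross-sectional SD it is about 15% to 55% for rho from 0 to 0.8, and 47% to 97% if d is per 1 SD of reserve. The direction is robust: under each set of assumptions tried, the reserve contrast has less power than the simple group contrast on change. That d of about 1.2 was the authors' actual basis cannot be concluded, since it is only back-solved.

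**What to change.** In SAMPLE SIZE, state that the 80% refers only to the voxel-level activation difference. Give the actual basis of the 12 per group (design, effect size, sidedness, threshold and correct citation), or say that it cannot be recovered. Do not insert d = 1.2 as if it had been the planning value.

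Add that with 13 completers per group the reserve-by-group contrast on change reaches 80% power (two-sided 0.05, single uncorrected measure) only for a slope difference of about 1.3 SD of change per SD of reserve.

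In STATISTICAL ANALYSIS, say that a non-significant reserve result is inconclusive, and that the reserve-by-group effect will be reported with its 95% interval for whichever connectivity measure is analysed. That measure must be named for this to be possible, since the plan now specifies no network, region or summary value.

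In RECRUITMENT AND ANALYSIS OF NON-PARTICIPANTS, qualify the reference to the power calculation in the same way.

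The cost is a less favourable power statement and one decision about the connectivity measure. No further patients or scans are needed.
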